3.3.1 Potential Risks

The primary risks of this study are the BWL therapy, the pharmacologic therapy with NB, the assessment procedures, and lack of efficacy.

BWL: BWL is an established and widely-used intervention for obesity. The only foreseeable risks include some mild discomfort or embarrassment when discussing eating patterns or body image concerns. Previous controlled clinical trials with similar interventions with large numbers of similar patients have not reported problems. Any troublesome effects would be readily identifiable by the experienced research clinicians during the repeated evaluations. Thus, the risks of BWL are judged to be minimal.

NB: NB combination is FDA-approved for the treatment of obesity. Both medications will be used in the present study. NB has demonstrated safety, tolerability, and efficacy for patients with obesity treated over much longer periods of time (>12 months) than in the present study (Greenway et al., 2010). NB was associated with the following side effects in 10% or more of the time and significantly greater than rate in placebo: nausea, headache, constipation, and vomiting. NB was associated with the following side effects less than 10% of cases but significantly more than placebo: dizziness, insomnia, dry mouth, and diarrhea. Less common side effects include risk of seizure, increase in blood pressure and heart rate, hepatotoxicity, and angle-closure glaucoma. Large studies (e.g., Greenway et al., 2010 with N=1742) reported that the proportion of participants reporting a serious adverse event did not differ between NB and placebo (1.6% versus 1.4%) and none of the observed events

were judged to be related to the study. In keeping with the FDA advisory pertaining to antidepressants, including bupropion, the following information will be included in the study consent forms:

"The U.S. Food and Drug Administration (FDA) has issued an Advisory cautioning health care providers, patients, and families to closely watch individuals taking bupropion for signs of their depression getting worse and for thoughts of killing or harming themselves, especially during the first several weeks that bupropion is being taken. Patients and their families should watch for and promptly report new symptoms. For example, report to the study doctor as soon as possible any signs of impulsivity (taking action or saying something without thinking first), agitation (feeling nervous or finding sitting still very difficult), and panic attacks (extreme fear without apparent reason)."

To monitor changes in depressive symptoms, patients will be asked to complete the PHQ-9 at monthly clinic visits. The research clinicians, who are trained and supervised by licensed psychologists in suicidal assessment, will review PHQ-9s during the clinic visit, and will ask pointed questions pertaining to suicidality/suicidal ideation (i.e., suicidal thoughts, plan, means, and intent) using the Columbia Suicide Severity Rating Scale. If it appears, based on the clinical judgment of the research clinician, that the participant is experiencing significant adverse effects of the medication, the investigators and study physician will be consulted and a determination of whether to discontinue the medication will be made. If warranted, the participant will be given a referral and safety planning will be implemented. If any participant experiences adverse reactions, or if side effects are too severe, the medication will be discontinued.

Assessments: Completion of the assessment procedures may cause some mild anxiety or embarrassment to some patients. Drawing blood from a vein to perform necessary laboratory tests is quite safe. Sometimes a bruise will occur at the puncture site and on very rare occasions a blood clot or infection may occur. If this occurs, appropriate treatment will be instituted immediately.

Failure to Improve: There is a chance that the patients will not lose weight or will gain weight during the study. Patients will be withdrawn from the study if their clinical condition deteriorates to a significant degree. Our experience with numerous RCTs is that this is quite rare.

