In the proposed RCT, our dosage follows standard and long-standing dosage for both naltrexone and bupropion used for related psychiatric problems. Per previous RCTs, a dosing escalation approach will be used [Greenway, Fujioka & Plodkowski, 2010; Wadden et al., 2011]. This dosing will continue for the remainder of the RCT unless a patient develops intolerable side effects. If such occur, the physician may reduce the dosing to achieve tolerability. If the patient cannot tolerate the medication, has adverse effects, or is non-compliant with medication for >7 consecutive days, they will be discontinued from the medication. Physician visits will be brief (10 -15 minutes), focusing on compliance with dosing and evaluating side effects. For participants taking medication for greater than 4 weeks, a 7-day taper will be provided.

Month 2	NB Medication	
Study Day	Naltrexone Capsule	Bupropion IR Capsule
1-7	--	150 mg once a day
8-study end	50 mg	150 mg twice a day

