6.2.3 Pharmacokinetics (if applicable)

6.2.4 Biomarkers (if applicable)

6.3 Study Procedures

Subjects will participate in an initial evaluation to determine eligibility. Eligible participants who provide written informed consent will start BWL treatment which last for three months. The BWL treatment is a mixture of the published LEARN behavioral lifestyle weight control treatment developed by Brownell (2000) and the Diabetes Prevention Program (Knowler et al., 2002); the PI and research team has extensive experience administering BWL with patients with obesity, binge-eating disorder, and histories of bariatric surgery. BWL will be delivered weekly by research-clinicians according to treatment manuals that detail session-by-session procedures. These manuals closely parallel patient-version BWL self-care materials for the entire course of treatment and follow closely that used by Wadden et al. (2011) in the COR-BMOD Trial testing BWL and NB/placebo medication for obesity, but modified for post-MBS patients. Behavioral strategies (goal-setting, self-monitoring, stimulus control problem-solving) will be taught within a lifestyle approach for achieving dietary goals (augmented by portion size and caloric goals) and physical activity goals (to achieve 180 min/week of moderate physical activity). Research-clinicians will be trained in BWL by the research team and will be supervised and monitored over the course of treatment delivery to ensure quality adherence. After one month of BWL treatment, "treatment response" will be determined based on early weight loss status because of its strong prognostic significance for optimal weight loss outcomes. Early weight-loss responders will continue BWL treatment, while *non*-responders will be given a pharmacologic agent (NB) to augment BWL treatment for the remaining two months of treatment. Outcomes assessments will be done by independent evaluators not involved in the treatment delivery and blind to responder status. Participants will be asked to complete self-report surveys at the baseline evaluation, monthly during treatment, and at the end of treatment. For participants starting NB medication, they will be asked to have labs drawn to examine liver values for safety before starting medication and again after being on the medication for one month.

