6.3.6 End of Study and Follow-up

Participants will be asked to attend a post-treatment (end of study) assessment, which will consist of an interview, measured weight, and completion of self-report surveys as indicated in the assessment schedule grid.

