6.3.7 Removal of subjects

Withdrawal/attrition from treatments will be examined. Use of other treatments during the study will be assessed and considered in analyses. Patients will be asked about all forms of treatments during major assessments. Criteria for removal of patients from the study may include worsening depression, suicidal ideation, or failure to comply with medication. Previous experience suggests that worsening clinical status is rare; in such cases, [name] and study physician would determine whether to remove the person from the study and provide referrals.

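### Study removal for deterioration or medication non-compliance has no stated follow-up of outcomes, so Month-3 PHQ-9 results can be slightly biased

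*Combined protocol and SAP*

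**What the plan says.** Two sections provide for exit from the study itself. Section 3.3.1 (Failure to Improve) states: "Patients will be withdrawn from the study if their clinical condition deteriorates to a significant degree". Section 6.3.7 states: "Criteria for removal of patients from the study may include worsening depression, suicidal ideation, or failure to comply with medication". In that section removal is a case-by-case decision: the "study physician would determine whether to remove the person from the study and provide referrals", together with a named investigator. Both sections describe deterioration as rare.

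Other sections stop only the drug. Under section 6.1.2, if a patient "has adverse effects, or is non-compliant with medication for >7 consecutive days, they will be discontinued from the medication". Section 3.3.1 (adverse reactions) and section 6.2.2 (pregnancy) likewise discontinue medication without mentioning study exit. Medication non-compliance therefore has two different stated consequences.

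PHQ-9 is a secondary outcome (5.2.2). PHQ-9, weight and adverse events are scheduled at baseline and Months 1, 2 and 3 (6.3.1). Section 6.3.6 says "Participants will be asked to attend a post-treatment (end of study) assessment" but does not say whether that includes someone already removed. The stated model, a linear mixed model, is for percent weight loss only (6.4.1). No PHQ-9 analysis is given, and the missing-data heading listed in the contents (6.4.5) has no text in the body.

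**The concern.** A removal rule that ends observation is different from one that ends treatment. Here one ground for ending observation, worsening depression, is what a secondary outcome measures. If the people whose PHQ-9 rises most are the ones with no Month-3 score, the Month-3 mean can look better than it was.

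The monthly measurement limits this, because "patients will be asked to complete the PHQ-9 at monthly clinic visits" and worsening found at such a visit is recorded before exit. It does not exclude it. Worsening can surface between PHQ-9 points: "BWL will be delivered weekly by research-clinicians according to treatment manuals", and the consent advisory says "Patients and their families should watch for and promptly report new symptoms".

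At stake is the accuracy of the effect sizes that the pilot is meant to pass to larger trials (1.1, 2.1, 3.2), and the adverse-event record of the people who fared worst.

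**Working it through.** The plan contains no sample-size calculation, PHQ-9 or weight SD, removal rate or expected number of NB starters. There is no figure to reproduce, and every input below is an assumption.

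**PHQ-9 inputs.** 12 NB starters out of N=25; change from baseline with true mean 0 and SD 5; correlation 0.6 between Month-2 and Month-3 change; removal after Month 2 at a rise of 8 or 10 points.

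**Expected exits.** Per person, 1 - Φ(8/5) = 5.5% and 1 - Φ(10/5) = 2.3%. Times 12, this is 0.66 and 0.27 exits per trial.

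**Standard error of a 12-person mean.** 5/√12 = 1.44 points.

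**Mixed-model shift.** Each of 20,000 simulated trials compares the likelihood estimate of the Month-3 mean (Month-3 change regressed on Month-2 change among those kept, then predicted for those removed) with the mean that full data would have given. Negative values favour treatment.

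| What triggers exit | Rise of 8 | Rise of 10 |
|---|---|---|
| Month-2 score, recorded before exit | 0.0 | 0.0 |
| Between-visit worsening, correlated 0.8 with both scores | -0.2 | -0.1 |
| The missing Month-3 score itself | -0.4 | -0.2 |
| Month-3 score itself, only half of such people removed | -0.19 | -0.09 |
| Recorded worsening, care after exit improves PHQ-9 by 3 points | about +0.17 | about +0.07 |
| Between-visit worsening (0.8), care improves PHQ-9 by 5 points | +0.06 | +0.02 |

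The third row is the extreme mechanism, because the trigger is the missing value itself. It is 0.4/1.44 = 0.28 and 0.2/1.44 = 0.14 standard errors. The second row is 0.14 and 0.07 standard errors. Under the extreme mechanism a Month-2 to Month-3 correlation of 0.4 gives -0.51 / -0.24, and 0.8 gives about -0.23 / -0.10. Taking 8 or 16 starters instead of 12 leaves the shift essentially unchanged. All values are averages that include trials with no exit.

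**Completer means.** No PHQ-9 model is stated, so a completer analysis is possible. If exit depends on the recorded Month-2 score, the shift is -0.6 × 5 × φ(c)/Φ(c):
- c = 1.6: -0.6 × 5 × 0.1109/0.9452 = -0.35.
- c = 2.0: -0.6 × 5 × 0.0540/0.9772 = -0.17.

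A completer mean therefore shifts even when the worsening was recorded.

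**Weight.** Assumed mean loss is 1% then 2%, SD 2 then 3, correlation 0.8, with removal at a gain of 3% / 5%. The mixed-model shift is 0.0 if recorded and +0.12 / +0.03 percentage points if not, against 3/√12 = 0.87. That is 0.14 / 0.03 standard errors.

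**Chance that it arises.** With 12 starters, 1 - (1 - p)^12 at p = 1%, 2% and 5% gives 11%, 22% and 46% for at least one such exit.

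**The case against.** The strongest reply is that this is a drafting gap with no practical consequence. The protocol usually stops the drug first, study removal is discretionary and called rare, and section 6.3.6 is not limited to people still on treatment. Withdrawal is to be examined (6.3.7), and retention is reviewed (7.12). The trial is an unrandomised, uncontrolled pilot of 25 people whose primary objective is feasibility and acceptability, and a fraction of a standard error in a secondary outcome changes no decision.

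Most of that stands, and it sets the low severity. It does not close the gap. Sections 3.3.1 and 6.3.7 refer to the study, not to treatment. Section 7.12 promises care, not outcome measurement. Counting exits as attrition does not supply the missing scores.

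A reader might infer three stronger things that the documents do not support:
- **That the bias always favours treatment.** Removed people are referred and supported (3.3.1, 6.3.7, 7.12). If that care helps, a model that extrapolates from recorded worsening is too pessimistic and the sign reverses.
- **That removal for medication non-compliance also flatters the result.** Nothing shows that these people would do worse, so the direction is unknown.
- **That the primary weight result is distorted.** Section 6.3.7 does not list weight gain as a ground. Section 3.3.1 mentions it only shortly before the phrase on clinical condition.

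**Conclusion.** The gap is real. Two sections permit exit from the study for reasons that can be the outcome itself, no section keeps the remaining assessments, and the rules on non-compliance differ between 6.1.2 and 6.3.7. Month-3 PHQ-9 results can be biased as a consequence, usually toward benefit when poor outcome drives exit and later care does not help.

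The size is small: under the main assumptions the mixed-model shift runs from about 0 to -0.4 points against a standard error of 1.44, with slightly positive values possible. The result rests on the assumed SD, correlations, thresholds and group size, and the -0.4 / -0.2 end also on the least favourable trigger. The shift does not shrink with more participants, which matters somewhat for effect sizes carried forward. Severity: could be changed; nothing in the trial depends on it.

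**What to change.** Amend sections 3.3.1 and 6.3.7 to separate stopping treatment from leaving the study:

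- Deterioration, worsening depression, suicidal ideation or medication non-compliance leads to stopping NB, and behavioural treatment too if clinically advised. The investigator and study physician decide, with referral as now. This also aligns 6.3.7 with 6.1.2.
- Unless consent is withdrawn, the person is still invited to the remaining scheduled PHQ-9, weight and adverse-event assessments. Remote attendance (already allowed in 6.3.5) and refusal are both acceptable.
- Take a PHQ-9 and a weight when the stopping decision is made.
- Include everyone who started treatment in the PHQ-9 and weight analyses, whatever treatment they completed.
- Report the number stopped for these reasons by group, with their last recorded values.

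The cost is a wording change in two sections and the consent text, one short assessment at stopping, and at most two already scheduled assessments (Months 2 and 3) per NB starter who stops. The downside is a small assessment burden on someone who is unwell, and some data will still be missing.

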3.3.2 Potential Benefits

Subjects will receive potentially beneficial weight loss treatment(s) that are empirically-supported. There is substantial importance in the knowledge to be gained in this study. Finding ways to identify, understand, and improve treatments for weight regain after MBS is critically important to address this important health problem. The dearth of treatment research with this subgroup, particularly with pharmacological methods, is strikingly at odds with the public health significance and prevalence of obesity and MBS. Given the modest risks associated with the treatments and study procedures and the substantial potential knowledge to be gained, the benefit to risk ratio is very favorable.

4 - Study Objectives

4.1 Hypothesis

We hypothesize that the treatments will be feasible and acceptable to subjects, and that subjects will experience significant weight loss and improvements in psychosocial functioning. More specifically, it is hypothesized that early responders to BWL will show weight loss during the trial, while the addition of NB will aid early non-responders in achieving weight loss.

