Pharmacologic Treatment. Another promising, yet understudied, avenue involves the use of weight-loss medications after MBS. Emerging research suggests utility in weight-loss medications after MBS (13). The combination of Naltrexone and Bupropion (**NB**), also known as "Contrave," is an optimal starting point due to its consistent weight-loss evidence base, affordable costs, tolerable side-effects, safety profile, and putative mechanisms of action. In 2014, the FDA approved NB for obesity following empirical support from several RCTs performed with obesity (14). These RCTs reported significant clinically-meaningful weight losses with naltrexone plus sustained-release bupropion combined in fixed-dose pills. These

findings supporting NB medication are consistent with large RCTs which reported greater weight loss with NB than placebo (-6.5 vs -1.2% (14)). Although the name brand (Contrave) is expensive, the combination of Naltrexone and Bupropion are available at affordable prices. Putative mechanisms of action for NB seem relevant for post-MBS patients who might also be struggling with maladaptive eating behaviors, such as loss-of-control (LOC) eating. LOC eating and related eating-disorder psychopathology are consistent predictors of poor outcomes after MBS (15). As reviewed in the preliminary data section below, NB may be helpful in both reducing problematic eating such as LOC eating (i.e., binge eating) and weight loss. Putative mechanisms of action for NB is especially relevant for reducing LOC eating and weight per hypothesized effects on brain regions implicated in the regulation of food intake and weight based on the mechanisms of action of leptin (16).

Early Weight Loss. Meaningful early weight loss, ranging from 0.5 to 3% weight loss during the first 1-2 months of treatment, is a consistent predictor of weight loss by the end of treatment and longer-term (17). Earlier work has found that at least 1% weight loss early in treatment was associated with meaningful weight loss at the end of treatment (17).

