6.2 Assessments

Assessment Procedures. **Table 1** summarizes the assessment schedule and measures. Assessments will be done by *independent* evaluators *not* involved in the treatment delivery and *blind* to early weight loss responder status.

Assessment of Treatment Outcome and Time Course.

Percent total weight loss (%TWL) (measured weight across time points). Per standard reporting guidelines, %TWL will be determined by the following formula: [(Initial Pre-Treatment Weight) — (Post-Treatment Weight)] / [(Initial Pre-Treatment Weight)]*100.

Psychosocial/Behavioral Functioning listed below.

Informed consent will be obtained after complete study description, followed by interviews and surveys.

Interviews:

Eating Disorder Examination Interview — Bariatric Surgery Version (EDE-BSV) (18) an investigator-based interview will be the primary method for assessing loss-of-control eating, as well as severity of eating-disorder psychopathology.

Mini International Neuropsychiatric Interview-Version 7.0 (MINI) (19) is a brief structured interview for psychiatric disorders, which will provide data to characterize subjects.

Anthropometrics: **Weight** and **height** will be measured to calculate body mass index.

Self-Report Measures (baseline and repeated per Table 1):

Demographics: ethnicity/race, age, sex, education, and socio-economic status.

Eating Disorder Examination-Questionnaire Version with Instructions (EDE-Q-I) (20), which generates the same eating behavior and pathology data as the interview version, will be used across *all assessment points* given its low burden (*in addition to the EDE-BSV given during major assessment points*).

Food Craving Inventory (FCI) (21) assesses general and specific food cravings (**relevant for NB**) and comprises four subscales for different food groups. The FCI has been validated and psychometrically supported in studies with obesity and BED. The use of this craving instrument will allow direct comparison to the leading NB non-surgical obesity trials (14).

Patient Health Questionnaire-9 (PHQ-9) is a brief and widely-used measure of depression in diverse medical settings (22). Post-MBS depression was associated with poorer MBS outcomes in some studies and is relevant to the study medication.

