6.3.1 Study Schedule

Assessment Points	Baseline	during rx 1-Month	during rx 2-Month	POST rx 3-Month
Medical History, Height, MINI Psychiatric Interview, Demographics (i.e., sex, race)	■			
EDE-BSV Interview, Treatment Credibility/Satisfaction	■			■
EDE-Q-I, FCI, PHQ-9, GPAQ, Weight, Adverse Events, Compliance	■	■	■	■

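### The responder weight-loss hypothesis is true by selection at Month 1 and favoured at Month 3, so a positive result says little about whether BWL works

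*Combined protocol and SAP*

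**What the plan says.** Section 4.1 holds that "it is hypothesized that early responders to BWL will show weight loss during the trial". The Synopsis and section 4.2 repeat the sentence. None of the three gives a time point, a size of loss, a comparator or a test.

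Section 6.3 says that response after one month of BWL "will be determined based on early weight loss status because of its strong prognostic significance for optimal weight loss outcomes". No cut-off is set for this trial. The nearest figures are in the background (section 2.1), which describes "Meaningful early weight loss, ranging from 0.5 to 3% weight loss during the first 1-2 months of treatment" as a predictor of later loss and reports earlier work in which "at least 1% weight loss early in treatment was associated with meaningful weight loss at the end of treatment".

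The outcome is defined in section 6.2: "Per standard reporting guidelines, %TWL will be determined by the following formula", and that formula takes the initial pre-treatment weight as both starting point and denominator. The schedule in section 6.3.1 lists weight at baseline and at Months 1, 2 and 3, so Month 1 is both the selection visit and an outcome visit.

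Section 6.4.1 plans whole-group %TWL, a mixed model with treatment group, time and their interaction, and a 95% CI for the non-responder arm. It names no interval or test for responders. Randomization is marked as not applicable (6.1.3), and there is no placebo (6.1.4).

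**The concern.** The variable that places a person in the responder group is part of the outcome used to judge that group. A responder has already lost weight during the trial when given the label. At Month 3, only regain of the whole qualifying loss within two months can turn that person's %TWL to zero or below. A positive responder mean is therefore expected even if BWL has no effect, provided average weight is stable.

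This is one of two specific weight hypotheses, it is repeated under the primary objective, and weight loss is a primary outcome (5.2.1). Sections 1.1 and 3.2 say the data will supply effect sizes for larger stepped-care trials. A responder mean that carries its own selection would be too large for that use if taken as the effect of BWL in unselected patients.

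**Working it through.** **The plan's own figure.** N=25 (5.3.1) comes with no alpha, power, effect size or SD, so there is nothing to reproduce.

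**Inputs from the documents.** N=25; selection on Month-1 loss; %TWL from pre-treatment weight; weights at baseline and Months 1, 2 and 3.

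**Assumptions.** True BWL effect zero; no average drift in the main case; cut-off c of 0.5% or 1% (section 2.1, background only); SD of one-month change 1.0 or 1.5 points. Two error models bracket the behaviour of weight:
- *Persistent*: monthly changes are independent and accumulate.
- *Fluctuation*: each visit, baseline included, varies independently around a stable weight.

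**Expected values.** With φ and Φ the standard normal density and distribution function:

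- Expected responders = 25 × [1 − Φ(c/SD)]
- Mean Month-1 loss in responders: M = SD × φ(c/SD) / [1 − Φ(c/SD)]
- Mean Month-3 %TWL in responders = b × M
- Mean change from Month 1 to Month 3 = (b − 1) × M

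Here b is the slope of Month-3 on Month-1 %TWL. It is 1 if changes persist. Under fluctuation with visit variance s², the two share only the baseline visit, so b = s²/(2s²) = 0.5.

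Example, c = 1 and SD = 1.5: φ(0.667) = 0.3194 and 1 − Φ(0.667) = 0.2525. Responders = 25 × 0.2525 = 6.3. M = 1.5 × 0.3194/0.2525 = 1.90. Month-3 mean = 1.90 (persistent) or 0.5 × 1.90 = 0.95 (fluctuation). Change from Month 1 to Month 3 = 0 or −0.95.

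| Cut-off % | SD | Responders | Month-1 loss % | Month-3 %TWL, persistent | Month-3 %TWL, fluctuation | Month 1 to 3, fluctuation |
|---|---|---|---|---|---|---|
| 0.5 | 1.0 | 7.7 | 1.14 | +1.14 | +0.57 | −0.57 |
| 1.0 | 1.0 | 4.0 | 1.53 | +1.53 | +0.76 | −0.76 |
| 0.5 | 1.5 | 9.2 | 1.53 | +1.53 | +0.77 | −0.77 |
| 1.0 | 1.5 | 6.3 | 1.90 | +1.90 | +0.95 | −0.95 |

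**Simulation of the same four settings** (N=25, trials with at least three responders, one-sample t test at two-sided 0.05 counted only in the stated direction, so 2.5% nominal):

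| Result over the four settings | Persistent | Fluctuation |
|---|---|---|
| Month-3 responder mean positive | about 98% | 94-96% |
| Month-3 loss falsely significant | 37-43% | 27-33% |
| Month-1-to-Month-3 loss falsely significant | about 2.5% | at most 0.1% |
| Month-1-to-Month-3 regain falsely significant | about 2.5% | about 28-33% |

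At cut-off 1% and SD 1.0, about 22% of trials have fewer than three responders and are left out. At 3%, the top of the background range, 0.6 of 25 or fewer would qualify at these SDs, so that case carries no information here.

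**Background regain.** Take c = 1, SD = 1.5 and regain of 0.5 points a month. A person then qualifies only if the random part of the Month-1 change is at least 1.5. Its mean in responders is 1.5 × 0.2420/0.1587 = 2.29.
- Persistent: 2.29 − 3 × 0.5 = +0.79 at Month 3; positive in about 78% of trials.
- Fluctuation: 0.5 × 2.29 − 1.5 = −0.36; positive in about 28% of trials.

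At 0.25 points a month the corresponding chances are about 91% and 70%.

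**The case against.** The best case for the plan has four parts.

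*The loss is guaranteed only at Month 1.* This stands. A reader might infer that the hypothesis is met automatically through the end of treatment and would look confirmed whatever BWL does. The documents do not support that. Participants are enrolled because they are regaining weight (5.3, 5.3.2), and the drift figures show that modest regain can erase the Month-3 result. Even without drift, formal significance would arise in fewer than half of null trials.

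*The plan specifies no responder test.* This also stands. The false-significance rates describe a test a reader might run, not one in section 6.4.1. But because no criterion is set, any positive responder figure can be read as agreement with the hypothesis.

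*No decision rests on this result.* Correct: nothing in the documents makes a responder result the basis for recommending BWL alone. A reader might draw that conclusion, but the plan does not. What remains is the stated use of the data for effect sizes.

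*The lead hypothesis concerns all subjects.* Correct, and whole-group %TWL does not condition on Month-1 loss, so this selection does not touch it. It does not test the responder clause either. Blinding assessors to responder status (6.2) does not remove the selection.

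**Conclusion.** The point holds in a limited form. The responder hypothesis is true by selection at Month 1 and favoured, not assured, at Month 3. With no BWL effect and no drift, the built-in Month-3 mean is +1.1 to +1.9% if changes persist and +0.6 to +1.0% if weight only fluctuates. These sizes rest on an assumed cut-off, SD and error model, none of which the plan supplies. The direction of the bias does not depend on the exact cut-off, provided it requires a loss and Month-1 and Month-3 %TWL are positively related, as their shared baseline makes likely. This is a weakness in how one hypothesis is worded and would be read, not a fault in the whole-group analysis.

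**What to change.** In the Synopsis, 4.1 and 4.2, replace the responder clause with an estimation aim: *we will estimate responders' weight change from Month 1 to Month 3 on continued BWL, with a 95% CI*. Add the interval to section 6.4.1. Report responders' baseline-to-Month-3 %TWL as description only, neither as confirmation that BWL works nor as an unselected effect size for later trials.

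State two limits beside the estimate. Re-basing removes the built-in loss, but regression to the mean may bias the change towards apparent regain (about −0.6 to −1.0 points if weight only fluctuates). Without a control, neither figure isolates a BWL effect.

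Do not reword the hypothesis as responders maintaining their loss. With no BWL effect and persistent changes, the mean holds or improves in about 50% of simulated trials and shows no significant regain in about 97%, so an inert programme would usually pass.

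The cost is a few sentences, since the weights are already scheduled (6.3.1). The downside is a smaller responder figure that may be near zero or negative.
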